QDRS Total	0.3 (0.5)	3.5 (2.7)	7.2 (5.1)	11.7 (6.9)	11.6 (7.8)	7.4 (6.3)	<.001
QDRS Cognitive Subscale	0.2 (0.3)	1.5 (0.9)	3.1 (1.9)	4.5 (2.6)	2.8 (2.3)	2.7 (2.4)	.005
QDRS Behavior Subscale	0.2 (0.3)	2.0 (2.0)	4.2 (3.5)	7.5 (4.9)	8.8 (5.9)	5.4 (4.8)	<.001

Although initially tested as an informant rating, we examined the utility of the QDRS as a PRO tool. We compared informant QDRS, patient QDRS, and Gold Standard CDR and CDR-Sum of Box in 254 consecutive dyads presenting to neurology clinics. The QDRS ratings were not considered in the Gold Standard evaluation and were completed prior to the office visit by the informant and patients. Cronbach alpha was examined as a measure of internal consistency. The internal consistency of the two versions of the QDRS were: Informant QDRS: 0.939; Patient QDRS: 0.922, supporting that both versions have excellent psychometric properties. Intraclass correlation coefficients (ICC) were used to assess interscale reliability comparing CDR domains, Sum of Box, and global scores with the QDRS correcting for chance agreement. The ICC examines the proportion of responses in agreement in relation to the agreement expected by chance. An ICC between 0.55 and 0.75 is considered good agreement, whereas an ICC greater than 0.76 is considered excellent.

The informant and patient versions of the QDRS have high degrees of agreement, and both versions show good to excellent agreement with Gold Standard CDR (Table 5).

We then looked at concurrent (criterion validity) comparing the mean performance on each Gold Standard measure of cognition (e.g., CDR, CDR-Sum of Box, neuropsychological testing), function (i.e., FAQ), behavior (e.g., NPI, Hospital Anxiety and Depression Scale), and caregiver characteristics (e.g., burden, depression) with the QDRS. Both informant and patient versions of the QDRS demonstrated strong relationships with clinical, cognitive and psychological variables. Strength of association was comparable to that seen for CDR and CDR-Sum of Box. Further, we compared the QDRS to ADRD biomarkers ([name] et al, manuscript under review 2020). Total QDRS scores as well as individual domain scores (e.g., memory, orientation, decision making, daily functioning) were significantly correlated with CSF Ab42, Ab42/tau ratios, PET PiB index, MRI total gray matter and hippocampal volumes (all  $p < .01$  correcting for multiple comparisons). The addition of the QDRS as a PRO to the PDM is an enhanced complementary approach to capturing real-world patient functioning, cognition, mood and behavior not routinely captured in the EHR, and provides important information regarding patients at the initial visit where EHR data may not be available.

**Table 5: Construct reliability between QDRS versions and CDR**

[figure not shown]
	Inf QDRS – Pt QDRS	Inf QDRS – CDR	Pt QDRS - CDR
Memory	.756	.754	.499
Orientation	.783	.787	.699
Decision making	.750	.728	.742
Activities outside home	.803	.862	.780
Activities inside home	.822	.861	.759
Personal hygiene	.918	.887	.855
Behavior	.716	-----	-----
Language	.839	-----	-----
Mood	.729	-----	-----
Attention	.749	-----	-----
Total QDRS	.887	-----	-----
QDRS-derived CDR-SB	.889	.909	.831
QDRS-derived CDR	.770	.826	.740

## D. RESEARCH APPROACH

**D.1. General Overview and Design (see figure):** Our research design is predicated on the notion that patient screening would appropriately identify a more targeted group for referral for appropriate diagnostic services. We will conduct three complementary studies to evaluate the effectiveness of the PDM, the QDRS or the combined (PDM + QDRS) approaches for early detection of ADRD. These approaches will be embedded within the EHR systems of diverse rural, suburban, and urban primary care practices in central Indiana and south Florida. The first study will be a clinical validation study (stage III) of the three approaches; the PDM, the QDRS, and the combination of both (the PDM + QDRS). The approaches will be clinically validated in real-world and diverse clinical settings in comparison to the gold standard of ADRD diagnosis used in the NIA-funded ADRD Research Centers across the nation. The gold-standard evaluations will allow us to determine the accuracy of the screening approaches and compare their performances. The other studies will be two independent pragmatic cluster-randomized controlled comparative effectiveness trials (phase IV) of the approaches embedded within the AWV (PDM within AWV, PDM + QDRS within the AWV) in comparison to the current AWV only process (AWV without PDM or QDRS). The two trials will be conducted in two separate healthcare systems; the first trial will be conducted at Eskenazi Health and within 12 months a second replicated trial will be conducted at University of Miami Health. Both trials will have identical methodology and would compare the performance of the three approaches in increasing the incidence rate of new ADRD subsequently documented in the EHR by the primary care practices.

**D.2. Clinical Setting for both the Clinical Validation Study and the Pragmatic Cluster-Randomized Controlled Comparative Effectiveness Trials:** All studies will be conducted in diverse rural, suburban, and urban primary care practices in central Indiana and south Florida. Such primary care practices include 10 federally qualified health centers affiliated with Eskenazi Health in Indianapolis and 10 primary care practices in South Florida affiliated with University of Miami (UHealth). Eskenazi Health is one of the largest safety net integrated healthcare systems in the nation serving underprivileged older residents of Marion County including African Americans (50%) and dual eligible Medicaid and Medicare

beneficiaries with a low socioeconomic status (50%). The UHealth has primary care practices serving older adults residing in Miami-Dade, Broward, and Palm Beach Counties and serving underrepresented groups of African Americans (19%) and Hispanic (45%) populations throughout South Florida. Our interdisciplinary research team has long-standing relationships with many sites in the two states. In late 2019, we published the results of a randomized controlled trial evaluating the

benefits and harms of ADRD screening among 4,000 older adults attending rural, suburban, and urban primary care practices.

**D.3. Subjects Recruitment into the Clinical Validation (Stage III) Study:** To recruit patients from the above clinical setting into our clinical validation study and using similar processes to our previous studies, trained research assistants will work with the practice manager from each primary care practice to identify potential subjects who meet the inclusion and exclusion criteria outlined in the table below. The research assistants will make initial contact via a phone or face-to-face at the primary care practices to garner interest in participating in the study and verify if the patient meets the inclusion criteria (see Table 6). Based on the literature, our own pilot data, and our power analyses (described below), we anticipate approaching 1,000 eligible subjects to enroll and complete data on 400 subjects. Rolling enrollment will take place over 18 months with an average monthly enrollment of 23 subjects per month.

Table 6. Inclusion and exclusion criteria	
Inclusion criteria	Exclusion criteria
65 years or older	Prior ADRD or mild cognitive impairment diagnosis as determined by ICD-10 code
At least one visit to primary care practice within the past year	Evidence of any history of prescription for a cholinesterase inhibitors or memantine.
Ability to provide informed consent	Has serious mental illness such as bipolar or schizophrenia as determined by ICD-10 code
Ability to communicate in English or Spanish	Permanent resident of a nursing facility
Available EHR data from at least the past two or three years	

**D.4. Primary Care Practices Recruitment into the Pragmatic (Phase IV) Trials:** We will approach the practice manager and the physician leader of each primary care practice to randomize their site into one of three early detection approaches; AWV and any other visit to the primary care physician or geriatrician without PDM or QDRS; AWV and any other visit to the primary care physician or geriatrician with PDM; and AWV and any other visit with the primary care physician or geriatrician with both PDM and QDRS. We have received approval from the leadership of both Eskenazi Health and UHealth. The PDM and the QDRS will be embedded within the AWV process for each practice. The current rate of using the AWV across the country is increasing from 14% in 2012 to more than 60% in our own practices. We will obtain a waiver of informed consent from the local Institutional Review Board to review retrospectively (after at least one year of screening) the EHR systems of each practice to calculate the annual rate of new ADRD diagnosis and other EHR data to measure processes of diagnostic assessment following the AWV including screening rate, referral rate for diagnostic assessments for early ADRD and patient acceptance rate of undergoing such assessments. In addition, we will interview the practice managers by implementing a one-time completion of Practice Transformation Assessment (PTA) for each clinic enrolled in the pragmatic trial at Eskenazi Health and University of Miami Health. This will be administered by the RA or Project Manager and completed by the Practice Manager. It will be variable, we will integrate it into our research method to describe the context of our healthcare system participating in our research. We want to know if there is any difference in the results between University of Miami Health (UMiami) and Eskenazi Health, and if that is related to different practice variable specifically the payment and healthcare transformation.

**D.5. Interventions and Control for the Pragmatic (Phase IV) Trials:** Our interdisciplinary scientific teams developed and tested both the PDM and the QDRS. Drs. [name] and [name] leveraged the widely available EHR data and the advantage of ML to develop the PDM with an approximate 80% accuracy for one-year and three-year prediction horizons. [name] team developed and tested the QDRS as a practical 2-3 minute patient reported outcome (PRO) tool for both early detection and staging of ADRD. Each pragmatic trial will randomize primary care practices into one of three approaches for early detection of ADRD at (1:1:1) ratio. These approaches include the current state of using AWV in primary care (the control group), the incorporation of the PDM into the AWV, and the combination of PDM and QDRS (Passive + QDRS). All of the three approaches will be implemented within the current Medicare funded AWV and will be integrated within the provider clinical encounter to accommodate the clinical flow and data capture and results display needs of the primary care practices. To randomly assign each practice to one of the three screening approaches, we will use a computer-generated randomization scheme.

**D.6. Integrating the PDM and QDRS within the Epic EHR:** We will leverage the processes and technologies currently and successfully in use every day in our clinical partner's primary care practices. These practices at both sites use Epic as their EHR and its related computerized decision support (CDS) engine and its patient-completed survey platforms. As indicated in the preliminary studies, EHRs contain detailed clinical data that can be accessed to run the PDM algorithm. EHRs also have a platform for patient reported outcome (PRO) survey in which we will integrate the QDRS for the selected primary care practices. The EHR-based CDS system will display the results of the screening to clinicians to promote the interpretation of the results by healthcare providers and patients. The Regenstrief Institute (see Resources section) has decades of experience in successful CDS research and implementation. Over the past three years, we have partnered with our Epic EHR clinical informatics colleagues to deploy various CDS tools such as patient reported surveys, predictive algorithms for social frailty, and deprescribing recommendations. These CDS tools provide clinicians with a graphical summary of the results with a focus on the factors driving these results. A similar approach will be adopted in this study, tailored through the extensive configuration options available in the Epic CDS engine. Patient registration at the primary care clinic would trigger the CDS process including patient completion of the QDRS. The CDS engine will also query the data sources for the required input features specific to the patient and invoke the PDM ML algorithm. Results will be displayed within the EHR user interface with an emphasis on the key features of the model that explain the final outcome for each individual patient, including actionable clinician-directed recommendations related to appropriate diagnostic work-up. The proposed workflow will be deployed in the two healthcare systems (Eskenazi Health and UHealth) and integrated within the flow of the primary care practices. We have received the approval from leadership at both sites for the deployment of both the PDM and the QDRS, as described in their letters of support. The technical infrastructure (including servers, EHR and CDS configuration options, and data connections) as well as the security and governance agreements already exist and therefore pose no threats to project objectives or risk of delayed timelines.

**D.7. Data Sources and Collection:** We will collect EHR data from all patients enrolled in the clinical validation study (identified data after obtaining informed consent from subjects) and from patients receiving care in all of the practices enrolled in the two pragmatic trials (de-identified data after obtaining consent from the practice leadership and receiving waiver from the IRB). For the clinical validation study, the research team will conduct a gold-standard ADRD assessment on all patients screened by the PDM and the QDRS.

**D.7.a. ADRD Diagnostic Assessment:** The ADRD assessment is modeled on the Uniform Data Set (UDS) 3.0 from the NIA Alzheimer's Disease Center program. The assessment will be performed face-to-face or via Zoom at research centers in Indianapolis and Miami. To accommodate subject preference, the assessment may be conducted at the subject's home for convenience. We have used such assessments for more than a decade with excellent quality assurance and completion. The ADRD assessment will include the following data that will be entered into a REDCap database, a browser-based, metadata-driven software and workflow methodology for designing clinical and translational research databases.

Subject interview and Medical Record Review will be used to collect information on demographics, primary language, alcohol/tobacco/substance use history, and family history. We will review the patient's medical records for the presence of comorbid conditions, medications, vitamin B12 level, thyroid test, syphilis tests, Complete Metabolic Panel (CPM) and brain imaging. When relevant to making a diagnosis and unavailable in the patient's record, laboratory tests or brain imaging – MRI, will be requested in collaboration with the primary care clinicians. Skilled nursing services will be utilized to perform blood draws with approximately 30ml of blood to be drawn from each patient, only one time.

Medical Evaluation: A detailed neurological examination will be completed by certified research staff. The Modified Hachinski Scale will assess vascular risks.

Cognitive Status: The Montreal Cognitive Assessment will be used for a global screen. The rest of the cognitive battery includes the Uniform Data Set (UDS) battery used in the NIA Alzheimer Disease Centers: 15-item Multilingual Naming Test (naming); Animal naming and Letter fluency (verbal fluency); Craft Story for paragraph recall testing of episodic memory (craft story immediate and delayed recall). ; Number forward and backward and Trail making A and B (processing and visuospatial abilities). The Geriatric Depression Scale is performed for assessment of mood.

Informant-Based Rating Scales: The CDR^73 will be used for global staging, the Neuropsychiatric Inventory (NPI) to assess behavior, and FAQ to assess activities of daily living.

Determination of Cognitive Status: Global rating scales will be combined with cognitive performance, Clinician Assessed Medical Conditions, Clinician diagnosis and medical record review to assign individuals to the following diagnostic categories after a consensus conference: No Cognitive Impairment (NCI), Subjective Cognitive Impairment (SCI), Mild Cognitive Impairment (MCI) or ADRD. MCI categories will be attributed based on the number of cognitive domains affected (single vs multiple; amnestic vs non-amnestic). ADRD cases will be assigned etiologies (AD, LBD, VaD, FTD, or mixed).

Professional research assistants will undergo a detailed training by Drs. [name] and [name] and will be certified in conducting the UDS assessment. Similar to our previous process from various research studies, we will use several incentives to encourage patients who screened positive to undergo the diagnostic assessment. First, we will work with the patient's physician to recommend the assessment. Second, the study personnel will provide information on the importance of the assessment. Third, the assessment will be offered free of charge. If transportation is a barrier, the patient will be offered free transportation or home-based assessment. Fourth, patients and their care partners will be reimbursed for their time with a \$50 gift for each.

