In response to the RFA-AG-20-051 call for the "validation, and translation of screening and assessment tools for measuring cognitive decline," our interdisciplinary scientific team is proposing to execute a clinical validation study, one pragmatic trial and one additional replicated pragmatic trial among patients from diverse rural, suburban and urban primary care practices in two independent sites located in central Indiana and south Florida. As required by the RFA, the first study will be a single-arm clinical validation (NIH Stage III) study of our developed early ADRD detection approaches; Passive Digital Marker (PDM) and the Patient Reported Outcome (PRO) tool, the Quick Dementia Rating System (QDRS) for discriminating gold standard ADRD diagnoses for a sample of 400 older primary care patients served in the two states. The other studies will be two pragmatic cluster-randomized controlled comparative effectiveness (NIH Stage IV) trials to incorporate the PDM and the QDRS within the Medicare paid Annual Wellness Visit (AWV) for a cohort of patients from practices across the two independent sites, with practices randomized in each pragmatic trial to one of the 3 arms (the AWV alone, the AWV with PDM, and the AWV with both the PDM and the QDRS).

These studies will support the following aims:

**Primary Aim 1:** Evaluate the predictive performance of the PDM, the QDRS, and the combined (PDM + QDRS) approach in the early detection of ADRD, compared to the gold standard diagnoses.

*Primary Hypothesis 1:* The Area Under the Curve (AUC) for the combined approach (PDM + QRDS) will be 0.85 or greater and the AUC for the PDM or the QDRS will be 0.75 or greater.

*Secondary Hypothesis 2:* The combined approach (PDM + QDRS) will have statistically better AUC than each individual approach alone.

**Primary Aim 2:** Evaluate the practical utility and effect of the PDM, the QDRS, and the combined approach (PDM + QDRS) in improving the annual rate of new documented ADRD diagnosis in primary care practices.

*Primary Hypothesis 1:* In comparison to the AWV alone, the combined approach (PDM + QDRS) within the AWV will increase the incidence rate of ADRD over the subsequent 12 months from 6% to 13%.

*Secondary Hypothesis 2:* In comparison to the AWV alone, the combined approach (PDM + QDRS) within the AWV will have higher acceptance rates for recommended ADRD diagnostic work-up following a positive screen from 44% to 66%.

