Potential problems & alternative strategies: The distributional assumptions for the binary outcomes are minimal, which will decrease the need to consider alternative analytic methods and models. However, to ensure the analytic methods appropriately account for the clustering effect when estimating standard errors and p-values, we will perform bootstrap estimation (i.e., using 1,000 datasets resampled with replacement at the person level) of the standard errors and confidence intervals surrounding the estimated values for AUC and % accuracy, and the estimated values for the difference in these values between screening approaches. In addition, if missing data occur, we will impute data using the simulation-based “Multiple Imputation” method, in which multiple complete datasets with plausible values for missing data are generated using model-based prediction, and analytic results from imputed datasets are aggregated to calculate appropriate standard errors and p-values in the presence of imputed data. We will use 100 imputed datasets, even though 10 to 50 are considered sufficient. Inclusion of potential auxiliary variables in the imputation model will be considered. A sensitivity analysis will be performed using participants with complete data.

**D.8.b. Primary Aim 2:** Evaluate the practical utility and effect of the PDM, and the combined methods in improving the annual rate of new documented ADRD diagnosis in primary care practices.

For Primary Hypothesis 1, three pragmatic screening approaches (AWV alone, AWV + PDM, and AWV + PDM + QDRS) will be compared on the annual incidence rate of EHR documented ADRD using nonlinear mixed models to account for clinic-clustered data. In the two pragmatic trials, different patients are randomized (via their clinics) to each of the 3 arms, making the outcomes independent between the three screening approaches; however, data will still be correlated for Aim 2 due to clustering of patients within clinics, which will be handled by random effects in the mixed models. We hypothesize the incidence rate will be 6% using AWV alone and 13% with the screening approach that combines AWV + PDM + QDRS. Incidence rates for all arms, including for AWV + PDM, will be calculated along with their 95% confidence interval.

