For Secondary Hypothesis 2, the analyses will be the same as described for Hypothesis 1 of Aim 2, except that the outcome will be acceptance rates for recommended ADRD diagnostic work-up following positive screen. We hypothesize the acceptance rate will be 44% using AWV alone and 66% with the screening approach that combines AWV + PDM + QDRS.

Potential problems & alternative strategies: Same as those described for Aim 1 above.

**D.8.c. Sample Size & Power:** Calculations were performed with PASS, a comprehensive power and sample size software. All calculations assume two-sided tests and alpha = 0.05. For study 1 (i.e., Aim 1), a sample size of 15 cluster pairs consisting of 400 persons (26.667 persons per cluster) will provide 81% power to compare population values of 75% versus 85% in the outcome of % accuracy of classification. This is based on using nonlinear mixed models to compare two paired (i.e., dependent) proportions. The proportions are considered dependent instead of independent because all three screening approaches for study 1 will be performed in the same sample of 400. This approach was selected because it will increase power by allowing participants to serve as their own controls. Moreover, it is appropriate for a diagnostic validity study to compare methods in the same sample (i.e., method contamination is not an issue). This calculation assumes that participants are recruited from 15 clinics (i.e., clusters) and that the within-pair coefficient of variation (CV) between clusters is .058. The CV was calculated as  $CV = \text{SQRT} (ICC \times (1 - \phi) / \phi)$ , where the intraclass correlation coefficient (ICC) was assumed to be 0.01, and phi is 0.75 (i.e. the proportion of accuracy for one of the standard screening methods). The power will be slightly greater than 81% to detect values of 75% versus 85% in the AUC, based on power for comparing two dependent AUC's, assuming discrete cutoff values, and accounting for a sample inflation factor (IF), where  $IF = [1 + (M - 1) * ICC]$ , M = average number of persons per cluster, and the ICC is 0.01.

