Because the other studies are two separate pragmatic clinical trials, participants will be cluster-randomized to three different arms. This approach ensures that rigorous testing of the outcomes (incident ADRD detection and acceptance of subsequent diagnostic assessments) is not contaminated by the other screening approaches in other arms of interest. In addition, the 400 patients in study 1 will be excluded from the two pragmatic trials to avoid contamination. The total sample for each pragmatic trial will be slightly over 2,600, if each of enrolled practice screen conservatively 175 patients per year for a total of two years of screening. Alternatively, the total sample size for each trial will be 3,600, if we recruit, as we have in past trials, 200 patients per clinic. The table below shows the power for comparing ADRD incidence and acceptance rates between two different arms under the conservative and historical recruitment scenarios. Calculations were based on using nonlinear mixed models to compare two independent proportions, assuming cluster randomization (i.e., level-2 randomization) and the

ICC is 0.01. The “AWV alone” arm is expected to have ADRD incidence of 6% and acceptance rate of 44%. The table shows that power will exceed 80% to detect ADRD incidence of 6% vs 13%, even under conservative recruitment projections, and power for comparing acceptance rates will be 99%.

Outcome	Conservative recruitment* (N = 2,600)	Projected (feasible historically) recruitment* (N = 3,600)
ADRD incidence 6% vs 13%	86%	89%
Acceptance 44% vs 66%	99%	99%

\*Conservative recruitment = Total of 2,600 patients with 866 patients and 5 clusters per each of 3 arms; power for pairwise comparisons based on 1,732 patients with 866 patients and 5 clusters per each of 2 arms, and M = 173.2 patients per cluster. Historical recruitment = Total of 3,600 patients with 1,200 patients and 5 clusters per each of 3 arms; power for pairwise comparisons based on 2,400 patients with 1,200 patients and 5 clusters per each of 2 arms, and M = 240 patients per cluster.

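### Aim 2 has one primary hypothesis and two separately powered trials, but no joint analysis, no health-system contrast and no rule for reading a split result

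*Combined protocol and SAP*

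**What the plan says.** The Specific Aims give Aim 2 one primary hypothesis: that the combined approach "will increase the incidence rate of ADRD over the subsequent 12 months from 6% to 13" per cent, compared with the AWV alone. It is not stated per trial. D.1 describes "two independent pragmatic cluster-randomized controlled comparative effectiveness trials", one in each health system, the second replicating the first within 12 months. It adds: "Both trials will have identical methodology and would compare the performance of the three approaches in increasing the incidence rate of new ADRD".

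D.8.c plans the sample size for each trial. It opens with "All calculations assume two-sided tests and alpha = 0.05", calls the trials separate ("Because the other studies are two separate pragmatic clinical trials, participants will be cluster-randomized to three different arms") and concludes that "power will exceed 80% to detect ADRD incidence of 6% vs 13%, even under conservative recruitment projections". The table gives 86% (conservative recruitment) and 89% (historical recruitment).

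D.8.b, the Aim 2 analysis, compares the three arms in a nonlinear mixed model. The only dependence it names is that "data will still be correlated for Aim 2 due to clustering of patients within clinics", handled by random effects. It does not say whether the model is fitted to each trial or to both together.

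D.4, after describing the practice-manager assessment, adds: "We want to know if there is any difference in the results between University of Miami Health (UMiami) and Eskenazi Health", and asks whether practice characteristics such as payment explain a difference. No model or contrast is attached to this.

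**The concern.** Two trials give two answers to one question, and the plan does not say how they combine. Aim 2 could be read as met if both trials are significant, if either is, if the first is, or if a pooled estimate is. These rules differ in power and false-positive rate. The second trial starts later, so an unwritten rule could be chosen after the first trial's results are known.

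The between-system question in D.4 also needs an analysis that spans both trials, and D.8.b offers none. Neither the Aim 2 paragraph on potential problems, which refers back to Aim 1, nor D.9 takes the matter up.

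**Working it through.** **Inputs.** Incidence 6% v 13%, ICC 0.01, 5 practices per arm per trial, 866 patients per arm with M = 173.2 (conservative) or 1,200 with M = 240 (historical), two-sided 0.05: all from D.8.c. The trials are independent (D.1).

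**1. The plan's own power.** Design effect 1 + (M − 1)(0.01) = 2.722 or 3.39. Variance sum 0.06×0.94 + 0.13×0.87 = 0.1695.
- Conservative: SE = √(0.1695×2.722/866) = 0.0231; 0.07/SE = 3.03; power 85.8% (stated 86%).
- Historical: SE = √(0.1695×3.39/1,200) = 0.0219; 0.07/SE = 3.20; power 89.2% (stated 89%).

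The stated figures reproduce.

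**2. Two independent trials, planned effect true in both.** With stated power p:

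| | p = 0.86 | p = 0.89 |
|---|---|---|
| Exactly one significant, 2p(1−p) | 24.1% | 19.6% |
| Both significant, p² | 74.0% | 79.2% |
| Neither, (1−p)² | 2.0% | 1.2% |
| At least one, 1−(1−p)² | 98.0% | 98.8% |

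With no effect in either system, the chance of at least one p<0.05 is 1 − 0.95² = 9.75%.

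A t test on 8 df (10 practices in two arms) lowers per-trial power to 76-80% and raises the exactly-one probability to 32-37%. For the secondary acceptance outcome, stated power is 99%, so both trials succeed with probability 0.99² = 98%. The issue therefore lies with the primary outcome.

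**3. One joint model, 15 practices per trial.** With 10 practices per arm over both trials, SE falls by the factor 1/√2 = 0.707, that is by 29%: 0.0163 (conservative) and 0.0155 (historical).
- 6% v 13%: 0.07/SE = 4.29 and 4.52; power 99.0% and 99.5% (normal), 98.2% and 99.0% (t, 18 df).
- 6% v 11%: variance sum 0.06×0.94 + 0.11×0.89 = 0.1543; per-trial SE 0.0220 and 0.0209, power 62% and 67% (normal). Jointly 89% and 92% (normal), 86% and 89% (t, 18 df).

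**4. Fewer practices.** The 15 per trial come from the footnote to the D.8.c power table. D.2 lists 10 practices in each system, and the D.10 text recruits 15 from the two sites. At 6% v 13%, with the same M:
- 10 per system (about 3.33 per arm per trial): per-trial SE = 0.0231×√(5/3.33) = 0.0283, or 0.0268; per-trial power 70-74% (normal). Exactly one significant: 2×0.70×0.30 = 42% to 2×0.74×0.26 = 38%. Joint power 94-96% (normal), 89-92% (t).
- 15 in all (5 per arm over both systems): joint power equals the per-trial figure in step 1, 86-89% (normal), 76-80% (t).

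**5. Arm-by-system contrast, 15 practices per trial.** The SE of the difference between two independent effects is 0.0231×√2 = 0.033, or 0.0219×√2 = 0.031. The 95% half-width is 1.96 times that, 6.4 or 6.1 percentage points. At 80% power (multiplier 1.96 + 0.84 = 2.80) it detects a between-system difference of about 9 points, more than the planned 7-point effect itself.

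**The case against.** The strongest reply is that two separate replicate trials, each reported at 0.05, are a legitimate and deliberate design. The power statement is made for each trial, and it reproduces. All of that stands. Three stronger readings are therefore not supported:

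- **That Aim 2 has only 74-79% power, or a 9.75% false-positive rate.** The first figure applies only if both trials must succeed, the second only if either suffices. No section sets either criterion, so neither shows that the D.8.c power claim is wrong.
- **That the plan tests each trial at 0.05 and rules out a joint analysis.** This is an inference from per-trial sample sizing. D.8.b is silent. If its model is joint, the split-result figures describe only the per-trial readings. If it is per trial, each trial sits in one health system, so a system term could not be fitted and its absence from that model is no fault. On either reading, something needed to answer Aim 2 is unstated.
- **That the trials would contradict each other.** A split means one p-value below 0.05 and one above, not effects in opposite directions.

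Two further objections have force. The sentence in D.4 may be meant as contextual, and the contrast is imprecise (step 5), so it should be an estimate and not a confirmatory test. Making a pooled test confirmatory in place of the replication would also be a real change of design, since it puts an average over two different populations first. The fix below avoids that.

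**Conclusion.** The gap holds in limited form. One primary hypothesis is answered by two separately powered trials, with no joint estimate, no between-system analysis and no rule for a split result. On the plan's stated power, with the planned effect true in both systems, a split has probability 20-24%. That rests on independent trials, 15 practices per trial, ICC 0.01 and the normal approximation; fewer practices or a t reference make a split more likely.

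A pre-specified joint model is worth having. At 6% v 13% its power is about 98-99% with 15 practices per trial and 89-96% with 10 per system. At 6% v 11%, with 15 per trial, it is 86-92% (t to normal) against 62-67% per trial (normal). With 15 practices in all, the joint analysis only recovers the power claimed for a single trial.

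This is an inexpensive improvement that should be made. It is not an error in the power calculation or a flaw in the replication design.

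**What to change.** In D.8.b:

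1. State that each trial is analysed on its own, with its estimate and 95% interval, as the planned replication.
2. Add one joint mixed model over both trials, with arm and health system as fixed effects and clinic as a random effect.
3. State, before the first trial is unblinded, how the per-trial and joint results together decide Aim 2, including when only one trial is significant. If the sponsor prefers to require both or accept either, say so and give that rule's power and error rate from step 2.
4. Add the arm-by-health-system contrast as the analysis for the D.4 question, reported as an estimate with its interval. Say in advance that about ±6 points cannot exclude sizeable differences.
5. Reconcile the practice counts in D.2, D.8.c and D.10, and recompute per-trial and joint power on the agreed number.

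The cost is SAP wording and a little more analysis of data already to be extracted; D.10 plans Aim 2 retrieval and analysis for both systems in the same period. The drawback is that the joint answer waits for the second trial.
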